5.3 Feasibility

The feasibility of answering the primary research question will be addressed after the first 150 patients have been randomized and delivered. The primary outcome rate in the usual care group will be presented to the Data and Safety Monitoring Committee (DSMC) without any comparison by group. The DSMC would be charged with making a recommendation regarding potential revision of the sample size in addition to addressing the feasibility of answering the primary research question.

5.4 Interim Analysis

The DSMC meets in person at least once per year and more often if recommended by the committee. Before each of the annual meetings, a formal detailed report will be written by the Biostatistical Coordinating Center (BCC) which presents all baseline variables, protocol adherence, side effects, all adverse events reported, as well as center performance in terms of recruitment, data quality, loss to follow-up and protocol violations.

Once sufficient patients have been accrued into the trial, the report will also include a formal interim analysis evaluating the primary outcome by treatment group. For this evaluation, a cohort of patients is chosen consisting of all patients randomized before a certain date so that the analysis cohort does not depend on gestational age at delivery.

The main statistical issue relevant to interim analysis is the problem of performing multiple tests of significance on accumulating data. For this trial, the group sequential method of Lan and DeMets will be used to characterize the rate at which the type I error is spent.³⁴ This method is flexible with regard to the timing of the interim analyses. It is expected that an interim analysis will be conducted at approximately 50% of the final sample size of 850.

Asymmetric stopping boundaries will be used for the Lan-DeMets procedure. The upper boundary which describes the stopping rule for benefit will be based on 1-sided type I error of .025 and the Lan-DeMets generalization of the O'Brien-Fleming boundary. The lower boundary will be based on a less stringent stopping rule: 1-sided type I error of .05 and the Lan-DeMets generalization of the Pocock type boundary.

It is often useful to calculate conditional power given the observed data to date, and conditional on the future data showing the originally assumed design effect. If this conditional power is low (under 10 percent) the DSMC may consider termination for futility if the accrual rate is slow with confidence that the Type II error is not greatly inflated.³⁵

It is recognized that any decision to terminate the study would not be reached solely on statistical grounds but on a number of complex clinical and statistical considerations.

5.5 Analysis Plan

All statistical analyses will be based upon the total cohort of patients randomized into the trial. Although data on some patients may be missing, all relevant data available from each patient will be employed in the analyses. Patients will be included in the treatment group to which they were randomly assigned regardless of compliance.

The primary analysis will consist of a simple comparison of binomial proportions. The relative risk and confidence interval will be reported. The individual components of the composite outcome will also be examined. If the treatment groups are found to differ on a pre-treatment factor known to be a risk factor for the outcome, the statistical analysis will adjust for these differences. An evaluation of treatment by center interaction will be included. An analysis adjusting by center also will be performed to ensure that center differences do not change the conclusion.

If the two groups show a difference in the incidence of the primary outcome, interactions will be evaluated and subgroup analyses conducted to determine whether the effect prevails throughout particular subgroups of patients. Indeed, NIH guidelines require investigators to evaluate consistency between the genders and across racial subgroups (see Section 5.5.1). It should be noted, however, that subgroup analyses have been greatly abused, particularly when there is no overall treatment difference.³⁶ There is a strong temptation to search for a specific subpopulation in which the therapy is nevertheless effective. Yusuf et al. concluded "the overall 'average' result of a randomized clinical trial is usually a more reliable estimate of the treatment effect in the various subgroups examined than are the observed effects in individual subgroups."³⁷ Thus subgroup analyses will be interpreted with care.

It is generally acknowledged that subgroup analysis that is pre-specified in the protocol has more validity than ad-hoc comparisons. The following factors will be considered for subgroup analysis, if there is a significant interaction between the factor of interest and the treatment effect.

- Race/ethnicity (see below)
- Gestational age at randomization (< 20 weeks and \geq 20 weeks)
- Cervical length at randomization (< 15 and \geq 15 -20 mm)
- Treatment with vaginal progesterone (as planned per usual care locally)
- Screening to randomization interval
- Debris/funneling on randomization ultrasound
- Obesity by BMI category
- Parity
- Bacterial vaginosis/Nugent score at enrollment—Nugent \geq 7 with pH > 4.4
- Prior cervical surgery including LOOP/ LEEP

Loss to follow-up will be defined as no information regarding pregnancy prior to 37 weeks. Those defined as lost to follow-up will not be included in the primary analysis. It is expected that the loss to follow-up rate will be very low. For trials conducted by the MFMU Network, the loss to follow-up rate has typically been under 2 percent. However, a sensitivity analysis will be performed including patients lost to follow-up with different assumptions regarding their outcome, to determine whether the results are robust.

Since many of the secondary endpoints are dichotomous variables like the primary outcome, standard statistical methods for rates and proportions will be appropriate. The Wilcoxon rank sum test will be used to compare continuous variables, and survival analysis methodology may be used to compare time-to-event variables.

In general, analyses of data will be conducted to address the primary and secondary research questions of the trial, and other interrelationships among elements of study data of interest to the investigators and of relevance to the objectives of the study.

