3.6 *Randomization Method and Masking*

Consenting women will be assigned to one of the two arms by using an internet based randomization system maintained centrally by the Biostatistical Coordinating Center (BCC).

The simple urn method will be used to generate the randomization sequences because it provides a high probability of balance in treatment assignments, it is unpredictable, and it allows an explicit randomization analysis to be conducted with relative ease. Randomization will be stratified by clinical site to assure balance between the two arms with respect to anticipated differences in the clinic populations and possible differences in patient management.

4 Study Procedures

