5.2 Sample Size and Power

A one-third reduction in preterm birth < 37 weeks was selected as being clinically meaningful. If it is conservatively assumed that the rate of preterm birth < 37 weeks in the progesterone arm is between 28% and 35%, then a sample of 850 women is sufficient to detect a 33% reduction in preterm birth at 90% power. In addition this sample size yields more than 80% power to detect a 30% reduction, assuming a type 1 error of 5% 2-sided.

Table 2. Sample Size for Various Outcome Rates and Effect Sizes

PTB rate in Usual care arm (%)	Total sample size for 30% reduction	Total sample size for 33.3% reduction
Power=80% ($\alpha=0.05$; $\beta=0.2$)		
28	810	640
30	740	590
32	680	540
35	600	480
Power=90% ($\alpha=0.05$; $\beta=0.1$)		
28	1080	850
30	990	790
32	900	720
35	800	640

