Appendix A Design Summary

A Randomized Trial of Pessary in Singleton Pregnancies with a Short Cervix

OBJECTIVE: To determine whether pessary reduces the risk of preterm birth in women with a singleton gestation and a short cervix.

ORGANIZATION

Clinical Centers: Magee, UAB, Ohio State, Utah, Brown, Columbia, Case Western, UT-Houston, UNC, Northwestern, UTMB-Galveston, UPenn
 Subcommittee: [name] (Chair)

DESIGN

Major Eligibility Criteria: ❖ Singleton gestation
 ❖ Gestational age 16⁰ to 23⁶ wks
 ❖ Cervical length ≤ 20.0 mm

Groups: ❖ Usual Care (may include vaginal progesterone)
 ❖ Arabin Pessary + Usual Care

Random Allocation: Standard urn design; 1:1 allocation

Level of Masking: Unmasked

Stratification: ❖ Clinical site

Sample Size: ❖ 850

Assumptions: ❖ Outcome event=delivery < 37⁰ weeks gestation or fetal loss
 ❖ Usual care group event rate =28%
 ❖ Pessary group event rate =18.67% (33.3% reduction)
 ❖ Type I error = 2.5% (two sided with one comparison)
 ❖ Power =90%

Interim Analysis: ❖ Lan-DeMets group sequential method

SCHEDULED EVALUATIONS / DATA COLLECTION

Pre-Randomization: ❖ Cervical length measurement by trained sonographer
 ❖ Pregnancy, exposure and medical history

Randomization: ❖ Vaginal sample, vaginal Gram stain and vaginal pH

Post-randomization: ❖ Phone call to assess patient symptoms and compliance within 7 days of randomization
 ❖ Every four weeks: study visit to assess symptoms and compliance
 ❖ Study visit between 24 and 32wks: vaginal sample, vaginal Gram stain and vaginal pH
 ❖ Digital exam to ensure appropriate pessary placement (pessary group)

Delivery: ❖ Patient questionnaire 8 weeks after randomization and again at 37 wks gestation.
 ❖ Pessary group: assessed for fit or replacement, as needed
 ❖ Delivery and neonatal data

MANAGEMENT PROTOCOL

Both Groups: ❖ Vaginal progesterone per usual care and rescue cerclage if needed

Pessary Group: ❖ Placement management from randomization to < 37 wks

OUTCOME MEASURES

Primary: ❖ Delivery or fetal loss prior to 37 wks

Secondary: ❖ Randomization to delivery interval
 ❖ Gestational age at delivery
 ❖ Neonatal morbidity and mortality
 ❖ Lower genital tract or urinary tract infection
 ❖ Physician interventions including bedrest, cerclage, labor inhibition therapy

TIMETABLE

Enrollment: ❖ September 2016 to October 2019
 Data Collection: ❖ September 2016 to October 2019
 Closeout/Analysis: ❖ October 2019 to September 2021

References

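### Randomization is stratified by clinical site, but the primary test, relative risk and interval ignore the stratum; the analysis is valid, and slightly conservative only if sites differ appreciably (minor, efficiency only)

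*Combined protocol and SAP*

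**What the plan says.** Section 3.6 gives the stratum and the reason for it: "Randomization will be stratified by clinical site to assure balance between the two arms with respect to anticipated differences in the clinic populations". Possible differences in patient management are given as a second reason. Appendix A lists clinical site as the only stratification factor and describes the scheme as "Random Allocation: Standard urn design; 1:1 allocation".

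Section 5.5 sets the headline analysis: "The primary analysis will consist of a simple comparison of binomial proportions". A relative risk and interval accompany it, and no stratification is named for any of the three. Center enters in two other places in the same section: "An evaluation of treatment by center interaction will be included", and "An analysis adjusting by center also will be performed to ensure that center differences do not change the conclusion". The method for the center adjustment is not named.

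Section 5.2 sizes the trial for the same unstratified comparison: "then a sample of 850 women is sufficient to detect a 33% reduction in preterm birth at 90% power". Section 5.4 expects one formal look, "It is expected that an interim analysis will be conducted at approximately 50% of the final sample size of 850", and does not name its test statistic.

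**The concern.** When randomization balances the arms within sites, differences between sites contribute little to the difference between arms. An unstratified variance still counts that between-site variation. If site event rates differ, the standard error is a little too large, the test rejects slightly less often than its nominal level, and the interval is slightly too wide. The sharper result is relegated to a supportive role.

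The protocol gives reasons to expect some spread. Vaginal progesterone follows local practice in both arms (Section 3.3), and screening practice varied across the network (Sections 2.3 and 8.2). What is at stake is a small amount of precision in the headline result.

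**Working it through.** **Inputs from the documents.** Usual care rate 28%, pessary rate 18.67% (relative risk 2/3), total 850, 1:1 allocation, power 90% (Section 5.2, Appendix A). Type I error is 5% two-sided (Section 5.2). Appendix A prints 2.5% labelled two-sided, which would need 1016 women, so 5% is used here. There are twelve centers (Section 7.1). Section 2.3 reports a 2014 survey of 35 sites at 14 centers.

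**Assumptions.** The between-site SD of the usual care event rate is 0, 5, 8, 10 or 15 points around 28%. There are 12 or 35 sites, equal or very unequal in size. The relative risk is 2/3 in every site. The urn starts with one ball per arm and adds one ball of the opposite arm after each draw. The documents fix none of these.

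**Step 1: the plan's own figure.** With mean rate 0.2333, difference d = 0.0933, A = √(2 × 0.2333 × 0.7667) = 0.5981 and B = √(0.28 × 0.72 + 0.1867 × 0.8133) = 0.5945:

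- n per arm = [(1.960 × 0.5981 + 1.2816 × 0.5945) / 0.0933]² = 429.5, so 430 per arm and 860 in total, against the stated 850.
- Power at 425 per arm = Φ[(0.0933 × √425 − 1.960 × 0.5981) / 0.5945] = Φ(1.265) = 89.7%.

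The design is an unstratified two-proportion calculation and reproduces within about 1%. Power at 870 is 90.36%, so near 850 one power point is worth about 30 women (20 / 0.66).

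**Step 2: how much variance lies between sites.** The share at the usual care rate is SD² / (0.28 × 0.72) = SD² / 0.2016. With perfect balance within sites, the unstratified test would have type I error 2[1 − Φ(1.960 / √(1 − share))]. This is the limit of its conservatism, because the urn balances only softly.

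| SD (points) | Share | Type I error at perfect balance |
|---|---|---|
| 5 | 1.2% | 4.9% |
| 8 | 3.2% | 4.6% |
| 10 | 5.0% | 4.4% |
| 15 | 11.2% | 3.8% |

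**Step 3: simulation with the urn within site.** There were 60,000 trials of 850 women per scenario, with site rates normal and clipped to 2-90%. The unstratified pooled z-test was compared with the Cochran-Mantel-Haenszel test. For site k with n women (n₁ pessary, n₀ usual care), x₁ and x₀ events and m = x₁ + x₀:

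- Z = [Σx₁ − Σ n₁m/n] / √Σ[n₁n₀m(n − m) / (n²(n − 1))]
- Relative risk = Σ(x₁n₀/n) / Σ(x₀n₁/n)

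Stratified minus unstratified power, in percentage points (paired standard error 0.04-0.07):

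| SD | 12 equal | 35 equal | 12 unequal | 35 unequal | Unstratified type I error |
|---|---|---|---|---|---|
| 0 | -0.09 | -0.38 | -0.15 | -0.42 | – |
| 5 | +0.03 | -0.19 | +0.03 | -0.32 | – |
| 8 | +0.27 | +0.01 | +0.39 | +0.01 | 4.78-4.87% |
| 10 | +0.61 | +0.34 | +0.53 | +0.23 | 4.60-4.74% |
| 15 | +1.50 | +1.24 | +1.49 | +1.16 | 4.15-4.39% |

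The stratified test held 4.8-5.1% at SD 8-15. The log relative risk interval narrowed by 0.3-1.5% at SD 8-10 and by 2.8-3.4% at SD 15. Independent repeat simulations agreed, and with them the power ranges become -0.5 to +0.1 at SD 0-5, -0.1 to +0.4 at SD 8, +0.2 to +0.6 at SD 10 and +1.0 to +1.5 at SD 15. A separate simulation with spread set on the logit scale gave an average estimated relative risk of about 0.665 under either analysis.

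**Step 4: pooling small sites.** With 35 unequal sites nested in 12 centers, the change by site, and then with sites under 20 women pooled within their center, was: SD 0, -0.53 and -0.18; SD 5, -0.43 and 0.00; SD 8, +0.07 and +0.35; SD 10, +0.35 and +0.43; SD 15, +1.07 and +1.03.

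**Step 5: sparse strata at the interim look (425 women).** With 35 very unequal sites, about 40-50% of looks contain a site with only one arm if every site is exactly half accrued, and about 90% if accrual order is random. On average only about 2-5 women are involved. With 12 sites, each half accrued, none occurred.

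**The case against.** The strongest reply is that this is a preference, not an error. An unstratified comparison after stratified randomization is valid. Section 3.6 gives balance as the purpose of stratifying, and the urn delivers balance whichever test follows. Section 5.5 already pre-specifies a center-adjusted analysis and a look at treatment-by-center interaction. Section 3.6 also notes that the urn permits a randomization analysis, although the plan does not commit to one.

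Much of this stands. The benefit depends on a spread the documents do not give. At SD 5, where sites do differ, stratifying gains nothing or loses slightly. At SD 8 with 35 sites the gain is nil, and most of the type I error estimates at SD 8 lie within two Monte Carlo standard errors (about 0.09 points each) of 5%. Gains above one point need SD 15, roughly site rates of 0-58% at two SDs. The 35-site case describes an earlier 14-center network; this trial has 12 centers.

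A reader might infer more: that ignoring the stratum biases the relative risk, inflates type I error, or leaves center differences unaddressed. The documents do not support any of these. The error runs in the conservative direction, and the center adjustment is in the plan.

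What the reply does not remove is that the lead result does not use the factor the design balanced on. The supportive analysis also has no named method, and it refers to center where the stratum is site.

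**Conclusion.** The point holds as a minor matter of efficiency. The primary analysis is valid, and no conclusion of the trial is at risk. It is slightly conservative only if site event rates differ by about 8-10 points SD or more. At SD 10 the power forgone is 0.2-0.6 points, at most about 18 women of 850 on the closed-form curve. At the extreme of SD 15 it is 1.0-1.5 points, up to about 47 women. If sites barely differ, the planned analysis is as good or marginally better. These sizes rest on the assumed spread, number and sizes of sites, on a constant relative risk, and on the assumed urn parameters. Nothing here calls for a change in sample size.

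**What to change.** In Section 5.5, make the primary analysis a Cochran-Mantel-Haenszel test with a Mantel-Haenszel relative risk and confidence interval, stratified by the randomization site. Pool sites with one arm or very few women (for example under 20) within their center. Fix the pooling rule before outcomes by arm are seen, since Appendix A gives "Level of Masking: Unmasked". Name the same test in Section 5.4 for the interim look, report the unstratified comparison as supportive, and keep 850.

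No extra women are needed. The change is a protocol amendment requiring Steering Committee and IRB approval, and DSMC approval if it counts as major (Section 1.3). The statistical downside is up to about 0.5 power point if many small sites barely differ, or 0.2 or less with pooling. If there are many very unequal sites, the pooling rule would be needed at most interim looks.

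If the sponsor prefers to keep the unadjusted headline, the smaller edit is to say why, name the method for the center-adjusted analysis, and state whether it uses site or center.

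### Section 5.5 does not say how the relative risk and its interval will be reported after an early stop for benefit, when the ordinary estimate is exaggerated

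*Combined protocol and SAP*

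**What the plan says.** Section 5.4 sets the benefit boundary: "1-sided type I error of .025 and the Lan-DeMets generalization of the O'Brien-Fleming boundary". The lower boundary is looser: "1-sided type I error of .05 and the Lan-DeMets generalization of the Pocock type boundary". On timing it says "It is expected that an interim analysis will be conducted at approximately 50% of the final sample size of 850". The interim cohort is defined by a randomization cut-off date. The section adds that a decision to stop would not rest on statistics alone.

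On the final analysis, section 5.5 says "The primary analysis will consist of a simple comparison of binomial proportions", followed by "The relative risk and confidence interval will be reported". It gives no confidence level and no critical value, and it does not refer back to the boundaries. It also bases all analyses on everyone randomized, which is a larger group than the interim cohort.

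The planning values are in Appendix A: "Usual care group event rate =28"% and "Pessary group event rate =18.67% (33.3% reduction"). Section 5.2 also considers a 30% reduction and usual-care rates up to 35%.

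**The concern.** A stop for benefit at half information requires an unusually large observed effect. Trials that stop are therefore selected for having overshot, and the ordinary relative risk they report is on average further from 1 than the truth. Section 5.4 deals with repeated looks for the test. Nothing does the same for the estimate.

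The size of the benefit matters here. Sections 2.5 and 2.7 justify the trial by conflicting results for spontaneous preterm birth before 34 weeks: an odds ratio of 0.18 in one trial and 1.12 in another. After an early stop, readers would take the headline relative risk and interval as the measure of how well the pessary works. If the method of adjustment is chosen only after a stop, the choice is open to the charge of being post hoc.

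**Working it through.** **Inputs.** From the documents: usual-care rate 28% (range to 35%), design RR 0.667, smaller effect RR 0.70, 850 women allocated 1:1, one look at about 50%, one-sided benefit error 0.025 with O'Brien-Fleming-type spending. My assumptions: a 95% interval, a look at exactly half information, the boundary followed as written, no loss to follow-up.

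**Reproducing the sample size.** The usual formula for two proportions (pooled variance under the null, no continuity correction) for 28% against 18.67%, two-sided 5%, 90% power gives 430 per arm, 860 in total. The plan has 850. With 425 per arm, power is 89.7% for a 33.3% reduction and 82.1% for 30%. The design is reproduced.

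**Boundary.** The spending function is α(t) = 2[1 − Φ(z₀.₉₈₇₅/√t)]. At t = 0.5 this is 2[1 − Φ(2.241/0.7071)] = 0.001525, so z₁ = 2.963. The final value is z₂ = 1.969, a two-sided nominal p of 0.0490.

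**What crossing requires.** With 60/212 events in usual care (28.3%), 34/212 in the pessary arm gives z = 3.04 and crosses; 35/212 gives z = 2.91 and does not. The largest observed RR that stops is then 34/60 = 0.567. With 74/212 (34.9%), 46/212 crosses (z = 3.02), RR 0.62.

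**Behaviour given a stop for benefit.** I took the exact joint binomial distribution at the interim (212 and 213 women) and conditioned on pooled z ≥ 2.963. The interval is log RR ± m·SE, with SE² = 1/x₁ − 1/n₁ + 1/x₀ − 1/n₀. The ordinary interval uses m = 1.96 and the repeated interval m = 2.963.

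| Usual-care rate | True RR | Chance of stop | Geometric mean reported RR | Ordinary interval misses | Repeated interval misses |
|---|---|---|---|---|---|
| 28% | 0.667 | 24.5% | 0.525 | 9.1% | 0.3% |
| 28% | 0.70 | 17.5% | 0.535 | 12.9% | 0.5% |
| 28% | 0.75 | 9.8% | 0.549 | 23.1% | 1.0% |
| 28% | 0.80 | 5.1% | 0.560 | 45.2% | 2.0% |
| 28% | 0.81 | 4.4% | 0.562 | 52.0% | 2.3% |
| 28% | 0.85 | 2.4% | 0.570 | 94.7% | 4.4% |
| 28% | 0.90 | 1.0% | 0.580 | 100% | 10.7% |
| 35% | 0.667 | 37.6% | 0.568 | 5.9% | 0.2% |
| 35% | 0.70 | 27.6% | 0.580 | 8.2% | 0.3% |
| 35% | 0.80 | 7.9% | 0.608 | 29.4% | 1.3% |

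**Timing.** At a 28% rate and RR 0.667, the ordinary miss rate is 23.9% for a look at 40% of information and 5.2% at 60%.

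**All trials, stopped or not.** In 1,000,000 simulated trials, including the lower boundary, the ordinary interval covers 95.0% at RR 0.667 and 94.0% at RR 0.80 (28% rate). The mean reported RR at the design effect is 0.646.

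**Adding women randomized after the cut-off.** A woman randomized between 16 weeks 0 days and 23 weeks 6 days takes about 13 to 21 weeks to reach 37 weeks. At 34 enrolments a month (section 8.2), that is about 13.1/4.35 × 34 = 103 to 21/4.35 × 34 = 164 women, before any time for data entry and review. I took 85 more per arm (170 in total) as an assumption and simulated stopped trials at a 28% rate:
- RR 0.667: mean reported RR 0.56, ordinary interval misses 9%, repeated interval 0.4%.
- RR 0.80: 0.62, 33%, 2.2%.
- RR 0.85: 0.64, 49%, 4.5%.

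**Final look.** Using 1.96 instead of 1.969 gives a one-sided benefit error of 2.55% instead of 2.50%.

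**The case against.** The strongest reply is that an interval need not be judged conditionally on stopping. Over all trials the ordinary interval covers about 94% to 95%, the O'Brien-Fleming boundary makes early stops hard, and section 5.4 says stopping is not automatic. The repeated interval is also over-wide at the design effect and leaves the point estimate uncorrected. All of this is true, and it limits the weight of the point. It does not answer it, because someone reading a stopped trial knows that it stopped.

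Second, the plan does not actually commit to an unadjusted interval. It is silent, and an ordinary interval is inferred from the simple comparison described. That is fair, but silence is itself the gap.

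Third, the total-cohort wording in section 5.5 would bring in later women and dilute the exaggeration. This stands: the mean RR at the design effect moves from about 0.53 to about 0.56 under my assumption, still below 0.667.

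Two stronger readings are tempting. A reader might infer that the interval after an early stop misses the truth about half the time. That needs a true RR near 0.80 to 0.81 at a 28% rate, an effect the plan does not assume. A reader might also infer that any observed RR of about 0.66 or lower would stop the trial. At the planned 28% rate it must be about 0.57 or lower.

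**Conclusion.** The point holds as a gap in reporting. At the plan's own effects, a stop for benefit is a realistic event (about 17% to 38% of trials across RR 0.667 to 0.70 and usual-care rates of 28% to 35%). On the interim cohort it would present a true one-third reduction as 43% to 47% on average, with an interval that misses 6% to 13% of the time instead of 5%. For weaker true effects the distortion given a stop is much worse, but such stops are increasingly rare.

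The documents do not support any claim that the trial's error control or overall coverage fails. The final-look mismatch is a negligible matter of consistency.

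The figures rest on a 95% level, one look at half information and a boundary that is followed. An earlier look would make the distortion larger and a later one smaller.

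**What to change.** Add to section 5.5, before any comparative interim data are seen, that if the trial stops at the benefit boundary the report will:

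1. state that the ordinary relative risk is likely to be exaggerated;
2. give, beside the ordinary interval, a repeated confidence interval using that look's benefit critical value (about 2.96 at 50% information);
3. give, as a sensitivity estimate, a relative risk corrected for the stopping rule by a named method, such as a conditional or bias-adjusted maximum likelihood estimate;
4. show results for both the interim cohort and the total randomized cohort.

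The text should tie item 2 to the benefit boundary. The lower boundary's value at the same look is about 1.87, and using it would narrow the interval. A stage-wise-ordered interval would not help, because at a first look it equals the ordinary one. At the final look, use the final boundary value (about 1.969 with one look at 50%, a 95.1% interval) so that interval and test agree.

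The cost is a few sentences and a few lines of code, with no extra patients or data. The downside is a wider second interval after a stop. For 60/212 against 33/212, log RR = ln 0.55 = −0.598 and SE = 0.194, so 0.38 to 0.80 becomes 0.31 to 0.98. That interval is conservative at the design effect (0.3% missed). In the scenarios checked it keeps at least 95% coverage given a stop up to a true RR of 0.85, but not at 0.90 (10.7% missed at a 28% rate), where a stop has about a 1% chance.

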3.2 Secondary Research Questions

Secondary research questions that this study will address are:

- Does treatment with the Arabin cervical pessary for women with a short cervix (≤ 20 mm) compared with usual care alter any of the secondary outcomes listed in Section 4.6, including:
 - Preterm birth less than 28 weeks, 32 weeks, or 35 weeks?
 - Neonatal morbidity or mortality?
 - Special care nursery admission?
 - Lower genital tract or urinary tract infection?
 - Physician interventions including labor inhibition, cerclage, and bed rest?
 - Alter the rates of inflammatory markers in cervicovaginal fluid?
- What is the acceptability of and compliance with the Arabin pessary as an adjunctive with vaginal progesterone?
- Are there specific subgroups in which treatment with the pessary is more efficacious? (See Section 5.5 for a discussion of subgroup analyses.)
-

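### Subgroup analysis of ten factors depends on an interaction test with no stated level or adjustment, and nothing commits the plan to reporting the factors that do not pass

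*Combined protocol and SAP*

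**What the plan says.** Section 3.2 makes subgroup benefit a secondary research question: "Are there specific subgroups in which treatment with the pessary is more efficacious". Section 5.5 sets two conditions for answering it.

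- **Condition on the primary outcome:** "If the two groups show a difference in the incidence of the primary outcome, interactions will be evaluated and subgroup analyses conducted". The stated aim is to learn whether the effect holds across subgroups.
- **Condition on each factor:** "The following factors will be considered for subgroup analysis, if there is a significant interaction between the factor of interest and the treatment effect".

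Ten bullets follow: race/ethnicity, gestational age at randomization, cervical length, planned vaginal progesterone, screening-to-randomization interval, debris or funneling, BMI category, parity, bacterial vaginosis, and finally "Prior cervical surgery including LOOP/ LEEP".

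No significance level is attached to the interaction tests and no adjustment across them is described. Section 5.2 gives a level, "assuming a type 1 error of 5% 2-sided", and Appendix A gives 2.5% two-sided, but both belong to the sample size for the primary comparison.

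Race/ethnicity stands apart. Section 5.5 notes that "NIH guidelines require investigators to evaluate consistency between the genders and across racial subgroups", and Section 5.5.1 gives subgroup power for it.

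The safeguards offered are pre-specification, a warning about misuse of subgroup analysis, a preference for the overall result, and this sentence: "Thus subgroup analyses will be interpreted with care".

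**The concern.** A condition of this kind selects before it reports. A factor moves on to subgroup analysis because its observed difference was large enough to cross a threshold, so the differences that emerge are biased upwards. With ten tests and no stated error control, at least one may well cross by chance.

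The rule also works against its own purpose. Consistency of effect is best shown by the factors where subgroups agree, and those are the ones for which the plan promises nothing, race/ethnicity apart.

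What is at stake is the answer to the Section 3.2 question in a positive trial. A device that works equally well across the listed factors could be presented as strong in one group and weak in another, without the other factors beside it for context.

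**Working it through.** **Inputs from the documents.** 850 women allocated 1:1; event rates 28% and 18.67%, so a relative risk (RR) of 2/3 (Appendix A); two-sided 5% for the primary test (Section 5.2); ten factors (Section 5.5).

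**Assumptions.** Each interaction is tested at two-sided 5%. The RR is uniform across subgroups. Each factor is binary, with prevalence between 10% and 50%. Interaction is tested by a Wald test on the log RR scale. The primary condition is met when the primary test has P < 0.05. The documents settle none of these points.

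**1. The plan's own figures.** The plan states no error rate for the interactions, so the check here is on the inputs. Per arm, n = [1.96·√(2p̄q̄) + 1.2816·√(p₁q₁ + p₂q₂)]² / (p₁ − p₂)². With p₁ = 0.28, p₂ = 0.1867 and p̄ = 0.2333, this gives 430 per arm, or 860 in total against the stated 850. Power at 850 is 89.7% against the stated 90%. The racial subgroup powers in Section 5.5.1 also reproduce at a 28% control rate: 94.6% (stated as above 90%) and 49.2% (stated as about 50%).

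**2. Chance of at least one false interaction, independent tests:** 1 − (1 − α)^10.

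| Level per test | Chance |
|---|---|
| 1% | 1 − 0.99^10 = 9.6% |
| 5% | 1 − 0.95^10 = 40.1% |
| 10% | 1 − 0.90^10 = 65.1% |

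**3. Primary condition and correlation between factors.** Simulation at 5% per test, 6,000 trials per row. The correlation is that of the latent variables generating the factors.

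| Scenario | Primary condition met | False interaction, given it is met | False interaction, all trials |
|---|---|---|---|
| RR 2/3, independent factors | 90% | 38–40% | 34–36% |
| RR 2/3, correlation 0.3 | 90% | 37% | 33% |
| RR 2/3, correlation 0.6 | 90% | 31% | 28% |
| No pessary effect (RR 1), independent factors | 5% | 45% | about 2% |

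**4. Exaggeration, even split (212.5 women per arm per level).** The variance term per woman is v = 0.72/0.28 + 0.8133/0.1867 = 6.93. The SE of the log ratio of RRs is √(2 × 6.93/212.5) = 0.255. To be selected, the ratio must exceed exp(1.96 × 0.255) = 1.65. The mean of |Z| given |Z| > 1.96 is 2.34, so a selected ratio averages about exp(2.34 × 0.255) = 1.82 when the truth is 1.0. The simulated median is 1.8–1.9.

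**5. How misleading the selected subgroup looks.** The median RRs in the two levels of a falsely selected factor were about 0.48 and 0.88, when both are truly 0.67. About 45% of false selections showed an RR of 0.90 or more in the weaker level. Per positive trial, with independent factors, that is 1 − (1 − 0.05 × 0.45)^10 = 20%. Direct simulation gave 16–20% across the correlation settings.

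**6. Cost of a Holm step.** For RR 0.5 against 1.0 in an even split, SE = √[(0.72/0.28 + 0.86/0.14)/212.5 + 2(0.72/0.28)/212.5] = 0.255, so z = ln 2/0.255 = 2.71. Power is Φ(2.71 − 1.96) = 77% at 0.05, and Φ(2.71 − 2.81) = 46% at 0.005, the level of the first Holm step over ten tests.

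**The case against.** A reader might infer that Section 5.5 means only significant subgroups will ever be shown. The text does not say that. Factors are to be considered for subgroup analysis under a condition; nothing states that the other interaction results will be withheld. The paragraph before the list has consistency as its aim, and race/ethnicity is an announced evaluation. What stands is the absence of a commitment.

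A reader might also infer a 40% chance of a spurious finding whenever the effect is uniform. That overlooks the primary condition, which is a real safeguard: with no pessary effect, a uniform effect too, it cuts the chance to about 2%. The 40% also needs a 5% level that the plan does not state, and independence, which is doubtful for pairs such as cervical length and funneling.

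Nor do the figures support saying that a uniform effect would often look close to nil in one subgroup. The 45% applies per false selection; per positive trial it is 16–20%.

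Finally, the factors are pre-specified, an interaction test is preferred to separate within-subgroup tests, and the plan urges caution. These points make a firm subgroup claim less likely. They do not control the error rate over ten tests or change which estimates are produced.

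**Conclusion.** The concern holds as a gap in error control and reporting for the subgroup question. At an assumed 5% per test with a uniform relative effect, about three to four positive trials in ten would yield at least one false interaction. Its ratio of relative risks would be near 1.8 when the truth is 1.0.

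The size depends chiefly on the unstated level (10% to 65% for levels of 1% to 10% with independent factors) and on correlation between factors. It also depends on the assumed prevalences and on the relative scale, since a uniform RR does not mean a uniform absolute effect. The primary analysis and its conclusion are untouched.

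**What to change.** In Section 5.5, remove the significance condition on presentation. When the subgroup analysis is done, report for all ten factors the RR in each level and the ratio of RRs with its 95% confidence interval, in one table, whatever the interaction P value. State that ten interactions were tested and describe the results as exploratory. The condition on the primary outcome need not change.

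The cost is SAP wording and one table. It needs no new data and loses no power.

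A Holm correction over the ten tests, before calling any subgroup difference established, is optional. With independent tests, 0.05/10 = 0.005 per test brings the chance of a false interaction down from 40.1% to 1 − 0.995^10 = 4.9%, at the loss of power shown in step 6. For exploratory tests that trade is a matter of judgement; full reporting deals with the selection without it.
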